## 11.3 Total number of subjects requested (including records and specimens):

39

## 11.4 If you are recruiting by study arm, please identify the arms of the study and how many subjects will be enrolled in each arm

Randomization: Subjects will be randomized using a random number generator using simple randomization into 1 of 3 research treatment groups, with approximately 13 subjects in each arm:  
 Group 1: Auricular semi-permanent (ASP gold) needles  
 Group 2: Intradermal (long) needles using J-type No. 2 (.18)x 15mm  
 Group 3: Pyonex Pink 1.5mm (0.2 x 1.5mm)

## 11.5 Please provide a justification for your sample size

The study is organized as a mixed effects, randomized design with repeated measures. Subject, gender and age are random effects as subjects are presumed to be a random representation of the population of adult male and female patients seeking treatment for this ailment and obtaining similar care at this and other Air Force medical treatment facilities. Time of repeated measure is a fixed effect as the pre- and post-therapy times cannot be generalized to other times. Needle group is a fixed effect as the needle employed cannot be generalized to other needles and conditions.

A priori power was assessed using G\*Power Version 3.1.9.3 using the DVPRS for effect size. [4] DVPRS mean (SD) pain intensity for a broad sample consisting of inpatients and outpatients suffering from acute and chronic pain has been found to be 4.4 (2.4). The minimal clinically important difference of an 11-point pain scale in patients as will be included in this study has been determined to be a 25% percent change in the score. [5] This difference, mean and SD were used for the DVPRS effect size.

A priori power analysis of the DVPRS variable using the statistical method described below indicates 10 subjects in each research group, for a total sample size of 30, will have a power of 0.44 to detect the minimal clinically important difference at alpha = 0.14.

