# 11.0

## Statistical/Data Analysis Plan

### 11.1 Statistical Considerations:

List the statistical methods to be used to address the primary and secondary objectives, specific aims, and/or research hypotheses. Explain how missing data and outliers will be handled in the analysis. The analysis plan should be consistent with the study objectives. Include any sub-group analyses (e.g., gender or age group). Specify statistical methods and variables for each analysis. Describe how confounding variables will be controlled in the data analysis

**Outcome Measures:** There are two outcome measures. The effectiveness outcome measure is the Defense and Veterans Pain Rating Scale (DVPRS). The DVPRS [1,2] consists of an 11-point numerical rating scale with 0 indicating no pain and 10 indicating severe pain. It has been confirmed for reliability and validity in measuring both acute and chronic pain, and is currently the standard for pain measurement throughout DoD and VA health systems. The DVPRS demonstrates linear scale qualities allowing parametric methods to be used. There will be four repeated measurements of the DVPRS: pre-acupuncture, post-acupuncture, 24 hours and one week post-therapy. The needle tolerance outcome will be measured using an in-house developed questionnaire. It employs 5-point ordinal scales to evaluate 12 post-therapy experiences or perception encompassing adverse outcomes, inconveniences, and satisfaction. There will be three repeated measurements: post-acupuncture, 24 hours and 1 week post-therapy.

**Missing Data and Outliers:** Outliers will be checked for clerical error. If improperly recorded, the data will be corrected, and, if found to be properly recorded, will be retained. Medians, means and ranges will be calculated and assessed to accommodate extreme observations. Subjects with missing data will be excluded from analysis and the estimated sample size seen below adjusted for this eventuality. Furthermore, an analysis of sample characteristics of retained and dropped subjects will be performed to determine whether bias has been introduced due to exclusion.

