**Sub-group Analysis:** Analysis will center on differences between the three needle groups. The three treatment groups will allow inferences to be made as to whether each group is statistically different from one another. Medication is a potential confounder, but will be addressed by standardizing the dosage of analgesics used by all subjects rather than as a variable in a general linear model with the needle group variable.

Null Hypotheses:

H01 — there is no difference in means of the DVPRS between needle groups; and

H02 — there is no difference in means of the DVPRS between repeated measures; and

H03 — there is no difference in the distribution of the tolerance ordinal scales between needle groups.

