## 11.2 Sample Size:

A priori power analysis was performed using the DVPRS variable as described below. The analysis indicates a minimum of 10 subjects in each needle group, for a total sample size of 30, will have a power of 0.44 to detect the minimal clinically important difference at alpha = 0.14. We will be recruiting a total of 39 subjects, which is inclusive of a 30% drop out rate to accommodate those that may be lost to the study or have missing data to achieve a final total of 30 subjects.

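### Power of 0.44 is stated without its inputs; the planned four-score needle comparison has about 0.26–0.30 at alpha 0.14 if the within-subject correlation is 0.5

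*Combined protocol and SAP*

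**What the plan says.** Section 11.5 takes a DVPRS mean of 4.4 and SD of 2.4 from a broad patient sample. It adds a minimal clinically important difference that "has been determined to be a 25% percent change in the score", and then says "This difference, mean and SD were used for the DVPRS effect size". The tool is G*Power, "Version 3.1.9.3 using the DVPRS for effect size". The size is "10 subjects in each research group, for a total sample size of 30", and section 11.2 says this "will have a power of 0.44 to detect the minimal clinically important difference at alpha = 0.14".

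Section 11.1 sets the data structure: "There will be four repeated measurements of the DVPRS: pre-acupuncture, post-acupuncture, 24 hours and one week post-therapy". The first null hypothesis there (H01) is that "there is no difference in means of the DVPRS between needle groups". Section 11.6 tests it by a mixed effects repeated measures analysis of variance. No adjustment for the pre-treatment score is described.

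None of these sections gives Cohen's f, the assumed pattern of the three means, the within-subject correlation, the number of scores entered, or which effect in the analysis of variance was powered.

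**The concern.** There are two questions. First, a single difference and SD give a standardized difference d for two groups. Turning that into f for three groups requires a pattern of means, and none is stated. Second, H01 as planned compares needle groups over four scores, one of them taken before any needle is placed. Random allocation allows no treatment difference at that time, so including it dilutes the group contrast.

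Power is the only quantitative support for the sample size. Section 9.3 presents the study as a pilot for a possible larger multi-site trial. A figure that cannot be checked from the stated inputs, and that does not describe the planned test, is a poor basis for that step or for interpreting a null result.

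**Working it through.** **Inputs from the plan.** Mean 4.4, SD 2.4, 25% difference (11.5); three groups, N = 30, alpha 0.14, power 0.44 (11.2, 11.5); four scores (11.1).

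**Assumptions not in the plan.** Equal correlation ρ between all pairs of scores, with 0.5 as the central value and 0.3–0.7 as the range. The 1.1-point difference is the largest gap among the three means and is present in full at every post-treatment time.

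**Formula.** For the between-groups test with m scores per subject, λ = N·m·f²/(1 + (m−1)ρ), referred to a noncentral F with 2 and 27 degrees of freedom.

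**Step 1: the plan's figure.** The difference is 0.25 × 4.4 = 1.1, so d = 1.1/2.4 = 0.458. The two-group conversion gives f = d/2 = 0.229. With m = 4 and ρ = 0.5, λ = 30 × 4 × 0.229²/2.5 = 2.52 and power is 0.442, which matches 0.44. The stated β/α is 0.56/0.14 = 4. Imposing that ratio on the same inputs returns alpha 0.1397 and power 0.4413, so this reconstruction fits both published figures.

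**Step 2: is it the only match?** No. With f = 0.216, power is also 0.44 at ρ of about 0.41 with four scores, or about 0.34 with three post-treatment scores.

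**Step 3: f for three groups.** With means 0, 0.55, 1.1, f = d/√6 = 0.187. With means 0, 0, 1.1, f = d√2/3 = 0.216. These are the smallest and largest values when the widest gap is 1.1, so 0.229 is out of reach.

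**Step 4: the pre-treatment score.** With no difference at one of four times, the four-score mean difference shrinks to 3/4 and λ to 9/16 of its value.

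| Test, alpha 0.14, N = 30 | f = 0.187, ρ = 0.5 | f = 0.216, ρ = 0.5 | Range over both f, ρ 0.3–0.7 |
|---|---|---|---|
| Four scores, difference credited at all four | λ 1.68, power 0.35 | λ 2.24, power 0.41 | 0.31–0.49 |
| Four scores as planned, none before treatment | λ 0.95, power 0.26 | λ 1.26, power 0.30 | 0.24–0.35 |
| Three post-treatment scores only | λ 1.58, power 0.34 | λ 2.10, power 0.40 | 0.30–0.45 |

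A simulation of 40,000 trials per scenario gave 0.260 and 0.296 for the second row.

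**Step 5: what correlation would rescue 0.44 for the planned test?** Power of 0.44 needs λ of about 2.5. With f = 0.216, λ = 30 × 4 × 0.216² × 9/16/(1 + 3ρ) = 3.15/(1 + 3ρ), so ρ is about 0.09. With f = 0.187 the numerator is 2.36, so even ρ = 0 falls just short.

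**Step 6: a check that needs neither f nor ρ.** Any between-groups calculation that reached 0.44 by crediting all four scores has λ of about 2.52. Multiplying by 9/16 gives 1.42, and power of about 0.32.

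**The case against.** The strongest reply is that no error in f is on the page. A reader might infer from the close match that the plan used a two-group effect size by mistake. The documents do not establish that: f and the correlation are unstated, and Step 2 shows that a valid three-group f reaches 0.44 at ordinary correlations, in one case with post-treatment scores alone and neither fault present. A reader might also run the corrections together and say that the design delivers 0.26–0.41. That range mixes two tests, because its upper end still credits the pre-treatment score, and it holds only at correlation 0.5. Both parts of this objection stand.

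The pattern of means is also open. If adjacent needles differ by 1.1 points (means 0, 1.1, 2.2), f = d√(2/3) = 0.374. Then λ = 30 × 4 × 0.374²/2.5 = 6.72, with power 0.77 when all four scores are credited. For the planned test λ is 6.72 × 9/16 = 3.78 and power about 0.57. Treating 1.1 as the widest gap is conventional and conservative, but it remains an assumption.

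Alpha may not have been a fixed input either, since β is exactly four times alpha. Holding that ratio at correlation 0.5, with four scores credited, f = 0.216 gives power 0.42 at alpha 0.145, and f = 0.187 gives 0.37 at alpha 0.157.

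Finally, this is a declared pilot that openly reports low power, and no design change follows. That limits the weight of the point.

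What the objection does not answer is the mismatch with the planned test. The post-treatment-only route to 0.44 describes a different analysis from the four-score comparison in sections 11.1 and 11.6.

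**Conclusion.** The point holds in limited form. The stated power cannot be verified from the plan, and the four-score test of H01 does not deliver it under the usual reading of the target difference. At alpha 0.14 and correlation 0.5 that test has power of about 0.26–0.30, and 0.24–0.35 across correlations 0.3–0.7. Reaching 0.44 would need a correlation of about 0.09 or below, which is implausibly low for repeated pain scores in the same person within about a week.

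This rests on 1.1 points being the largest gap among the three means, equal correlations, 10 analysed subjects per group, the full difference at all three post-treatment times, and no baseline adjustment. The two-group conversion is the likely source of 0.44, but it should be put to the sponsor as a question rather than reported as a documented mistake.

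**What to change.** In sections 11.2 and 11.5, state f with the assumed pattern of the three means, the within-subject correlation, the scores counted and the effect powered. Then restate power for three groups at alpha 0.14:

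- about 0.26–0.30 for the four-score group test as now planned; or
- about 0.34–0.40 if H01 is changed to compare only the three post-treatment scores (0.30–0.45 for correlations 0.3–0.7). In that case sections 11.1 and 11.6 should say so.

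The first two figures in each case assume correlation 0.5; if the sponsor has a better value, it should be used and cited. Keep N as it is for a pilot. The only cost is a less favourable stated figure, with no extra subjects or visits.

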## 11.6 Data Analysis Plan: Complete description: Background, Objectives, Design, Step by Step how the project is going to be done, Data analysis plan:

Sample and needle group means, standard deviations, medians, interquartile ranges (IQR) and ranges will be calculated for interval variables. Frequency distributions will be produced for nominal and ordinal variables.

The null hypotheses H01 and H02 for the DVPRS outcome measure will be tested by a mixed effects repeated measures analysis of variance (rANOVA). In the event a null hypothesis is rejected, contrasts will be used to investigate effects and differences between and within research and time groups. Null hypotheses H03 will be tested with Chi Squared or Fisher's Exact tests. The significance level of multiple comparison tests will be corrected to  $\alpha = .05$  by the Holm method. [6]

[name], Senior Research Biostatistician Subject Matter Expert for Clinical Research Management under contracts OMNI 0004 3-82 and OMNI 0005 3-126, is the statistical consultant supporting this study. Statistical analysis will be performed with R Version 3.5.1. [7]

[6] Holm, S. 1979. A simple sequential rejective multiple test procedure. Scand. J. Statistics, 6: 65-70.

[7] R Core Team. R: A language and environment for statistical computing. R Foundation for Statistical Computing, Vienna, Austria. 2016 URL <http://www.R-project.org/>.

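### N = 30 is justified by power 0.44 at alpha 0.14, a level the analysis plan assigns to no test; at its only stated level, .05, the same pair implies power of about 0.25

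*Combined protocol and SAP*

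**What the plan says.** Section 11.2: "The analysis indicates a minimum of 10 subjects in each needle group, for a total sample size of 30, will have a power of 0.44" for the minimal clinically important difference (MCID) on the DVPRS, at alpha 0.14. Section 11.5 repeats the pair: 10 per group "will have a power of 0.44 to detect the minimal clinically important difference at alpha = 0.14". It gives the ingredients of the effect size as a mean of 4.4, an SD of 2.4 and a 25% change. It does not give the resulting f or the correlation among the four repeated DVPRS measurements. It refers the reader forward to the statistical method.

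That method is in section 11.6. H01 ("there is no difference in means of the DVPRS between needle groups", section 11.1) and H02 are tested by a mixed effects repeated measures ANOVA, with no significance level given. Then: "In the event a null hypothesis is rejected, contrasts will be used to investigate effects and differences". The only level in the section comes last: "The significance level of multiple comparison tests will be corrected to" .05, by the Holm method.

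**The concern.** A power figure describes a test at a stated level. Here the level used for power (0.14) is given to no test in the analysis plan, and the level in the analysis plan (.05) was not used for power. The omnibus test of H01 lies between the two with no level of its own, although it decides the effectiveness comparison and controls access to the contrasts.

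Two things are at stake. First, the decision rule for H01 is open: a p-value between .05 and .14 is a rejection on one reading and not on the other. The study is unblinded, so the level should not be left to be settled at analysis. Second, a reader planning the larger multi-site trial would take 0.44 as the pilot's power under its analysis plan. At .05 that is too high by about three quarters (0.44/0.25 = 1.76).

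**Working it through.** **Inputs from the documents.** N = 30 in three equal groups, power 0.44, alpha 0.14 (11.2, 11.5); mean 4.4, SD 2.4, MCID 25% (11.5); m = 4 DVPRS measurements (11.1); repeated measures ANOVA for H01, and .05 by Holm for multiple comparisons (11.6). The effect size f and the correlation r are not given.

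**Step 1: reproduce the stated figure.**
- MCID = 0.25 × 4.4 = 1.1 points, so d = 1.1/2.4 = 0.458.
- Assume the two-group conversion f = d/2 = 0.229, and r = 0.5.
- For the between-group F test with 2 and 27 df, λ = f²·N·m/(1 + (m − 1)r) = 0.229² × 30 × 4/2.5 = 2.521 (unrounded f).
- Power is 0.442 at 0.14, which matches 0.44, and 0.250 at .05.

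So the 0.44 is not a miscalculation. It is power at a different level.

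**Step 2: move the pair to .05 without assuming f or r.** Solve for the λ that gives power 0.44 at alpha 0.14, then evaluate the same λ at .05.

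| Stated pair | λ | Power at .05 |
|---|---|---|
| 0.44 at 0.14 | 2.504 | 0.249 |
| 0.435 at 0.145 (low end of rounding) | 2.38 | 0.238 |
| 0.445 at 0.135 (high end of rounding) | 2.63 | 0.259 |

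f and r enter only through λ, and the pair fixes λ. For example, f = 0.229 with r = 0.51, f = 0.216 with r = 0.41 and f = 0.187 with r = 0.23 each reproduce 0.44 at 0.14, and each gives 0.249 at .05. Using the degrees of freedom of other F tests gives 0.248 to 0.255.

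**Step 3: how often the choice of level changes the verdict on H01.**
- No difference between needles: 0.14 − 0.05 = 0.09.
- Difference at the MCID: 0.44 − 0.249 = 0.19.

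**Step 4: the contrasts, if H01 is tested at 0.14.** Take λ = 2.504, 27 df, and a contrast between the two most distant groups, averaged over time. Assume Holm over three pairwise contrasts, so the first step is .05/3 = .0167.

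| Position of third mean | Noncentrality | Power at .0167 | Power at unadjusted .05 |
|---|---|---|---|
| Midway | √λ = 1.582 | 0.186 | 0.332 |
| At one extreme | √(0.75λ) = 1.370 | 0.137 | 0.262 |

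No Holm step is more lenient than .05, so these contrasts stay below 0.44 at every step.

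**Step 5: sensitivity to a three-group effect size.** The f = d/2 conversion belongs to two groups. If 1.1 points is the range of three means, f runs from d√(1/6) = 0.187 (third mean midway) to d√2/3 = 0.216 (third mean at one extreme). With the λ formula of step 1, and r assumed, power at .05 is:

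| r | f = 0.187 | f = 0.216 |
|---|---|---|
| 0.3 | 0.22 | 0.29 |
| 0.5 | 0.18 | 0.23 |
| 0.7 | 0.15 | 0.19 |

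**The case against.** The strongest reply is that the text can be read without contradiction. Section 11.5 ties the power calculation to the method that follows, which for the DVPRS is the ANOVA; .05 is worded for multiple comparisons only. On that reading the omnibus test is at 0.14 and the contrasts at Holm .05. The study is also a pilot, its low power and lenient alpha are printed openly, no go/no-go rule depends on H01, and the plan never claims 0.44 for contrasts.

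Part of this stands. The 0.25 applies only if H01 is tested at .05. The contrast figures cover pairwise group means averaged over time with a Holm family of three; 11.6 also plans contrasts over time, which were not computed, and gives no family size. Pilot status can excuse low power, and a pilot may prespecify a lenient level.

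But prespecifying means writing the level down, and 11.6, the section that defines the test, does not mention 0.14. On the lenient reading, the 14% gate is undeclared and the between-group contrasts that would show which needle differs still fall short of 0.44. The value may not even have been chosen as a test level: the stated pair has β/α = 0.56/0.14 = 4, and a calculation that fixes that ratio on the step 1 inputs returns alpha 0.1397 and power 0.441. That is an inference, but it is a reason to ask for the level to be stated.

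**Conclusion.** The concern holds. The level behind the sample size is assigned to no test, and the level for H01 is missing. At .05, the only testing level in the plan, the stated pair implies power of 0.249 (0.238 to 0.259 with rounding). This rests only on an F test with 2 and 27 df and on the stated pair, not on f or r. At 0.14, pairwise contrasts between the extreme groups have power 0.14 to 0.19 at the first Holm step and 0.26 to 0.33 at unadjusted .05, on the assumptions in step 4. If a three-group f is used, power at .05 could be anywhere from 0.15 to 0.29 for correlations of 0.3 to 0.7, which the documents do not let a reader narrow. The 0.44 itself is reproducible; the fault is the mismatch of levels, and it must be corrected because the effectiveness hypothesis has no defined decision rule.

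**What to change.** - **Section 11.6:** state one significance level, 0.05, for the omnibus test of H01 and for the Holm-adjusted contrasts. If the investigators do intend 0.14 for H01, the section has to say so and acknowledge the 14% false-positive rate at the gate.
- **Sections 11.2 and 11.5:** replace the 0.44/0.14 pair with the power at the level set in 11.6, about 0.25 at .05 on the inputs that the pair implies.
- **Section 11.5:** print the three-group effect size f and the within-subject correlation. If f = d/2 = 0.229 was used, recompute with a three-group f and the stated correlation, and report that result instead.

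The cost is wording in three sections and no extra patients. The downside is that the stated power becomes less favourable.

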## 11.6 Data Analysis Plan: Complete description: Background, Objectives, Design, Step by Step how the project is going to be done, Data analysis plan:

Sample and needle group means, standard deviations, medians, interquartile ranges (IQR) and ranges will be calculated for interval variables. Frequency distributions will be produced for nominal and ordinal variables.

The null hypotheses H01 and H02 for the DVPRS outcome measure will be tested by a mixed effects repeated measures analysis of variance (rANOVA). In the event a null hypothesis is rejected, contrasts will be used to investigate effects and differences between and within research and time groups. Null hypotheses H03 will be tested with Chi Squared or Fisher's Exact tests. The significance level of multiple comparison tests will be corrected to  $\alpha = .05$  by the Holm method. [6]

[name], Senior Research Biostatistician Subject Matter Expert for Clinical Research Management under contracts OMNI 0004 3-82 and OMNI 0005 3-126, is the statistical consultant supporting this study. Statistical analysis will be performed with R Version 3.5.1. [7]

[6] Holm, S. 1979. A simple sequential rejective multiple test procedure. Scand. J. Statistics, 6: 65-70.

[7] R Core Team. R: A language and environment for statistical computing. R Foundation for Statistical Computing, Vienna, Austria. 2016 URL <http://www.R-project.org/>.

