##### **Goals**

1) Begin to identify which of 3 needles is most efficacious for BFA treatment of pain; 2) Identify patient experiences and tolerance of three commonly used acupuncture needles at Mike O'Callaghan Military Medical Center at Nellis Air Force Base. This study will compare 30 patients (10 per needling group) and will serve as a pilot study for a potential larger randomized control trial (RCT) across multiple MTFs in the Defense Health Agency (DHA) to establish better BFA care practices. We will be recruiting a total of 39 subjects, which is inclusive of a 30% drop out rate to accommodate those that may be lost to the study or have missing data to achieve a final total of 30 subjects.

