##### **Hypothesis**

1) There is a difference in BFA effectiveness and tolerance between ASP, long, and pyonex needles for the treatment of acute MSK pain. 2) Pyonex needles are the most effective and tolerated acupuncture needle for the BFA treatment of pain.

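### The test planned for the five-point tolerance items ignores their order; an ordinal test would detect a shift in tolerance more often with the same subjects

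*Combined protocol and SAP*

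**What the plan says.** Section 11.1 describes the tolerance questionnaire: "It employs 5-point ordinal scales to evaluate 12 post-therapy experiences or perception encompassing adverse outcomes, inconveniences, and satisfaction". It adds: "There will be three repeated measurements: post-acupuncture, 24 hours and 1 week post-therapy". The null hypothesis for this outcome, H03, is that "there is no difference in the distribution of the tolerance ordinal scales between needle groups".

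Section 11.6 gives the analysis: "Null hypotheses H03 will be tested with Chi Squared or" Fisher's exact tests. It names no rank-based or ordinal test. For description, "Frequency distributions will be produced for nominal and ordinal variables". On multiplicity, "The significance level of multiple comparison tests will be corrected to" 0.05 by the Holm method, without listing the tests that form the family.

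In section 9.3, the second goal is to "Identify patient experiences and tolerance of three commonly used acupuncture needles", and the second hypothesis is that "Pyonex needles are the most effective and tolerated acupuncture needle for the BFA treatment of pain". The sample size sections (11.2 and 11.5) plan for 10 analysed subjects per arm and give power for the DVPRS only, none for tolerance.

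**The concern.** Chi-squared and Fisher's exact tests return the same p-value if the five answer levels are shuffled, so they discard the ordering that the questionnaire records. Saying that one needle is the best tolerated means that its answers lie further towards the favourable end. The expected benefit in section 9.6, that other needles may be better tolerated than ASP, is of the same kind. A general test spreads its power over every way in which three distributions can differ, and little is left for a shift when there are only 10 subjects per arm.

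The pilot is meant to inform a larger multi-site trial, and tolerance is its second goal. Missing a real shift that the collected data could have shown is an avoidable loss.

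**Working it through.** **Inputs from the documents.** Three arms, 10 analysed per arm (11.2, 11.5); five ordered levels, 12 items, three times (11.1); Holm to 0.05 (11.6). With 10 subjects over five levels, the average expected cell count is 10/5 = 2, so exact or permutation p-values are needed.

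**The plan's own power figure.** It concerns the DVPRS, not tolerance. The difference is 25% of 4.4 = 1.1; d = 1.1/2.4 = 0.458; f = d/2 = 0.229. For the between-groups test with N = 30 and four measurements, λ = N·f²·m/(1+(m−1)ρ). Taking ρ = 0.5 (an assumption; the documents give no correlation), λ = 30 × 0.0525 × 4/2.5 = 2.52. At alpha 0.14 this gives power 0.442, against the stated 0.44. There is no corresponding figure for H03 to reproduce.

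**Simulation for H03.** Assumed effects: proportional-odds shifts, logit P(Y ≤ k) → logit P(Y ≤ k) − ln(OR). From a uniform baseline, an odds ratio of 5 gives .048/.070/.113/.214/.556, a mean shift of 1.16 categories; 3 and 8 give 0.84 and 1.40. Assumed baselines: uniform; .35/.30/.20/.10/.05; its mirror image; .1/.2/.4/.2/.1. Arms were 10 each (simple randomization may give unequal arms), with 1,500 trials per setting. P-values were exact, by full enumeration of the 3×5 tables. Monte Carlo standard error is at most 0.013.

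Null rejection at 0.05 was 0.037-0.053 for Fisher, 0.037-0.060 for exact Chi-squared and 0.046-0.061 for Kruskal-Wallis. All are close to their level.

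Power for one item at one time (ranges over the baselines):

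| Shift | OR | Threshold | Fisher | Kruskal-Wallis |
|---|---|---|---|---|
| One arm | 2 | 0.05 | 0.07-0.09 | 0.12-0.13 |
| One arm | 3 | 0.05 | 0.11-0.14 | 0.21-0.26 |
| One arm | 5 | 0.05 | 0.24-0.31 | 0.42-0.51 |
| One arm | 8 | 0.05 | 0.44-0.45 | 0.62-0.72 |
| Graded (1, √OR, OR) | 3 | 0.05 | 0.11-0.12 | 0.18-0.21 |
| Graded | 5 | 0.05 | 0.20-0.22 | 0.32-0.39 |
| Graded | 8 | 0.05 | 0.31-0.36 | 0.47-0.58 |
| One arm | 5 | 0.05/36 | 0.03-0.04 | 0.05-0.09 |
| One arm | 8 | 0.05/36 | 0.07-0.10 | 0.12-0.23 |

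The threshold 0.05/36 = 0.0014 is the first Holm step if each item is tested at each time (12 × 3 = 36). That count is an inference; the plan does not state it. Exact Chi-squared was close to Fisher (0.12-0.14, 0.25-0.30 and 0.41-0.45 at odds ratios 3, 5 and 8). Kruskal-Wallis was higher in all 28 shift settings at both thresholds.

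**Cross-check.** A separate simulation with Monte Carlo and permutation p-values (2,000 trials per setting, three baselines, one arm shifted) gave Fisher against Kruskal-Wallis 0.12-0.15 v 0.24-0.26 at odds ratio 3, 0.24-0.28 v 0.46-0.50 at 5 and 0.43-0.48 v 0.68-0.72 at 8. With 13 per arm, uniform baseline and odds ratio 5, it gave 0.37 v 0.60.

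**Arms differing in spread only.** Two arms at .1/.2/.4/.2/.1. With the third at .4/.1/0/.1/.4, Fisher 0.73 v Kruskal-Wallis 0.07; with the third at .3/.15/.1/.15/.3, 0.33 v 0.07.

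**The case against.** The planned tests are valid, hold their level and match H03 as written, and the first hypothesis in section 9.3 is also a non-directional difference. On that view the choice of test is a preference about which alternative to target. This is true, and it is why the point is one of efficiency.

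Proportional-odds shifts suit rank tests, so winning in every shift setting is expected. The ranking reverses when arms differ in shape: besides the spread examples above, one two-peaked arm (.3/.1/.1/.4/.1) against two central arms gave Fisher 0.30 v 0.06. Such patterns are possible, since the items mix adverse outcomes, inconveniences and satisfaction, and the questionnaire is not in the documents. This stands as the real price of the change. The planned frequency tables would still show such patterns.

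The gain is small for modest effects: 0.04-0.07 at odds ratio 2. For an item with 80% of answers in the lowest category it was 0.06 v 0.07 at odds ratio 2 and 0.13 v 0.17 at 3, although 0.28 v 0.41 at 5. Under a 36-test Holm family few conclusions would change. This also stands.

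A three-group Kruskal-Wallis test does not itself show that one needle is the best tolerated. That is correct, so pairwise follow-up is needed. For two arms of 10, uniform baseline and odds ratio 5, unadjusted pairwise power was 0.28 for Fisher and 0.45 for the rank test, so the advantage carries over before the Holm adjustment.

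Finally, how 12 items at three times become a test of H03 is left open, and changing the test does not settle it. That is so, and the fix includes it. If items were not corrected against each other, the chance of at least one false positive in 36 independent tests would be 1 − 0.95³⁶ = 0.84, and lower with correlated answers. That is not the most natural reading of section 11.6, and the main point does not rest on it.

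**Conclusion.** The concern holds as a loss of efficiency, not an error. For shifts in tolerance with 10 per arm, an ordinal test adds 0.07-0.13 to per-item power at odds ratio 3, 0.14-0.24 at 5 and 0.18-0.27 at 8 (one arm shifted, 0.05), with no inflation of false positives beyond simulation error. The direction held for every baseline tried. The sizes rest on assumed odds ratios, baselines, equal arms and one table per item per time. They apply to shifts only; for differences in spread alone the planned tests are clearly better. Neither test gives good power for modest shifts in a pilot of this size.

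**What to change.** - **Section 11.6:** test H03 with an ordinal method, either Kruskal-Wallis with exact or permutation p-values or proportional-odds regression. Follow it with Holm-adjusted pairwise rank tests. State that each item is analysed separately at each time; pooling the three times in one table would break independence.
- **Section 11.1:** word H03 as no shift in tolerance between needle groups, so that the hypothesis matches the test.
- **Clarification:** list the tests that the Holm family covers.
- **Optional:** name one lead tolerance measure in advance and report the other items and times through the frequency distributions already planned. A lead measure at a single time could miss either insertion or wear tolerance, because section 10.1 has long needles removed after 15-30 minutes while ASP stay in for 2-8 days and Pyonex for 2-21 days.

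The cost is wording in two sections, with no added subjects, visits or data. The price is a narrower H03 with little power for differences in spread, which the frequency tables would have to show descriptively.
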